#### 9.6.2.2. 80-Week Active Treatment Extension Phase

Efficacy analyses for the 80-week Active Treatment Extension Phase will be performed based on subjects who received at least one dose of active treatment (200 mg PO QD or 400 mg PO QD) during the 80-week Active Treatment Extension Phase. The efficacy endpoints will be summarized with descriptive statistics by treatment group. Continuous efficacy endpoints will be summarized using mean, SD, median, minimum, maximum, and number of observations analyzed. Binary efficacy endpoints will be summarized with counts, percentages, and associated 95% CIs for the percentages within each treatment group based on Clopper-Pearson method.

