**Table 1: Study Objectives (Continued)**

**Table 1: Study Objectives (Continued)**

**Table 2: Idiopathic Pulmonary Fibrosis Study Endpoints**

Endpoint	Name	Description	Timeframe
Primary	Forced vital capacity (FVC)	Percentage point difference in % predicted FVC	Baseline to Week 24
Secondary	FVC	Absolute change and rate of decline in FVC (expressed in mL)	Baseline through Week 24
Secondary	6-minute Walk Test (6MWT) with Borg Scale	Change in the distance walked during the 6MWT as measured in meters (m) Change in dyspnea rating on Borg Scale	Baseline to Week 24; Baseline to Week 52; Baseline to Week 76; Baseline to Week 104; Week 24 to Week 52; Week 24 to Week 104
Secondary	Disease progression	Disease progression is defined as one or more of the following: 
 
• Death from respiratory failure, or
 
• Absolute decrease of <math>\geq 10\%</math> from baseline in % predicted FVC at two consecutive evaluations at a minimum of 4 weeks between evaluations, or
 
• Decrease from baseline of <math>\geq 50</math> meters in 6MWT distance (in the absence of a readily explainable cause, such as injury or trauma), or
 
• Unexplained worsening hypoxemia (an absolute decrease from baseline of 4% or more in arterial oxygen saturation by pulse oximetry [SpO2]).
 
	Baseline through Week 24
Secondary	Quality of life	Change from Baseline in total score and domains on the Saint George's Respiratory Questionnaire (SGRQ)	Baseline through Week 24
		Change from Baseline in the University of California San Diego Shortness of Breath Questionnaire (UCSD- SOBQ)	Baseline through Week 24

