### 3. OVERALL STUDY DESIGN

#### 3.1. Study Design

This is a Phase 2, multicenter, multinational, double-blind, randomized, placebo-controlled study evaluating the efficacy, safety, [REDACTED] quality of life [REDACTED] of two oral (PO) treatment doses of CC-90001 (200 mg and 400 mg QD), compared with placebo, for an initial 24 weeks of treatment, in subjects with IPF. This study will also assess the efficacy and long-term safety in the 80-week Active Treatment Extension Phase when all IPF subjects will receive CC-90001 (200 mg or 400 mg PO QD). This study is designed to assess response to treatment by using measures of lung function, disease progression, fibrosis on radiography, and patient-reported outcomes, including cough, dyspnea, and quality of life assessments. It will also assess dose response.

Approximately 165 adult male and female subjects with a diagnosis of IPF (Lynch, 2018) will be randomized 1:1:1 (55 subjects per arm) to treatment with CC-90001 (200 mg or 400 mg PO QD) or matching placebo for an initial 24 weeks. Subjects receiving concurrent protocol-allowable standard of care (SOC) therapy are eligible to participate in the study. Approximately 75 subjects (25 subjects per arm) receiving protocol-allowable SOC are to be enrolled in the study. The randomization will be stratified based on the concurrent administration of protocol-allowable SOC (Yes/No). Subjects not receiving concurrent protocol-allowable SOC therapy will also be stratified by previous exposure to either pirfenidone or nintedanib (Yes/No).

[REDACTED] Subjects completing 24 weeks of treatment will continue onto the 80-week Active Treatment Extension Phase. Subjects who enter and complete the 80-week Active Treatment Extension Phase will receive treatment for a total of 104 weeks (Figure 1).

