g Spirometry, DLCO, and pulse oximetry will be assessed as part of the safety assessments for those subjects who discontinue for progressive disease during the 24-Week Double-blind Placebo-controlled and 80-Week Active Treatment Extension Phases.

- i Blinded IP will be packaged in 32 tablet-count, 16-day blister cards (16-day card includes IP for two additional days in the event the subject is unable to return for their scheduled visit).
  - On Visits 2 and 3, one blister card will be dispensed to the subject. Remaining IP from the blister card issued on Visit 2 will be reissued to the subject along with a new card on Visit 3. The subject should be instructed to finish the remaining IP in the blister card issued at Visit 2 before starting the new blister card issued at Visit 3.
  - On Visits 4 to 8, two blister cards will be dispensed to the subject per visit.
  - On Visits 9 and 10E, one blister card will be dispensed to the subject. Remaining IP from the blister card issued on Visit 9 will be reissued to the subject along with a new card on Visit 10E. The subject should be instructed to finish the remaining IP in the blister card issued at Visit 9 before starting the new blister card issued at Visit 10E.
  - On Visits 11E to 16E, two blister cards will be dispensed to the subject per visit.
  - On Visit 17E to 24E, three blister cards will be dispensed to the subject per visit.
  - On Visit 25E, two blister cards will be dispensed to the subject per visit.
- j Final dose of IP administered at the investigative site.
- k For all subsequent visits, an administrative window of  $\pm 3$  days is permitted. Scheduling of Visits 3 to 9 is based on Visit 2 (randomization date) and scheduling of Visits 10E to 26E is based on Visit 9 (re-randomization date). The Post-treatment Observational Follow-up Visit is scheduled 28 days (4 weeks) after the date of the last dose of IP  $\pm 3$  days.
- l If a subject has adequate documentation of successful treatment for either latent or active TB, the QuantiFERON-TB Gold test is not needed. Instead, a chest radiograph, obtained within the 12 weeks prior to Screening or during Screening, without changes suggestive of active TB infection as determined by a qualified radiologist, will be sufficient to permit further participation in the study for these subjects. Documentation of adequate treatment for TB must be obtained prior to randomization.

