### 9.7.2. Disease Progression

A subject will have met the criteria for disease progression when one or more of the following events have occurred:

- Death from respiratory failure, or
- Absolute decrease of  $\geq 10\%$  from baseline in percent predicted FVC at two consecutive evaluations at a minimum of 4 weeks between evaluations, or
- Decrease from baseline of  $\geq 50$  meters in 6MWT distance (in the absence of a readily explainable cause, such as injury or trauma), or
- Unexplained worsening hypoxemia (an absolute decrease from baseline of 4% or more in SpO2).

Subjects who experience an absolute decrease of  $\geq 10\%$  from baseline in percent predicted FVC at two consecutive evaluations at a minimum of 4 weeks between evaluations must be discontinued from the study IP and enter the Post-treatment Observational Follow-up (see Section 11.1). Example: a subject whose FVC decreases from 50% predicted at Visit 2 to 40% predicted at Visits 4 and 5 must be discontinued from the study. Whether to discontinue a subject from study treatment who experiences: 1) a decrease from baseline of  $\geq 50$  meters in 6MWT distance (in the absence of a readily explainable cause, such as injury or trauma), or 2) a new or worsening hypoxemia (an absolute decrease from baseline of 4% or more in SpO2), is at the Investigator's discretion.

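### Late extension means come from subjects selected for not having lost FVC, and the observed-value summaries planned in Section 9.6.2.2 neither correct for this nor label it

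*Combined protocol and SAP*

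**What the plan says.** Section 3.1 makes extension efficacy an aim: "This study will also assess the efficacy and long-term safety in the 80-week Active Treatment Extension Phase". Table 2 lists change in 6MWT distance and Borg score as secondary endpoints, with timeframes that include "Baseline to Week 104; Week 24 to Week 52; Week 24 to Week 104". The FVC endpoints visible in Table 2 end at Week 24. Part of that table is not shown, so later FVC endpoints may exist, and Table 5 schedules spirometry at every extension visit.

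Section 9.6.2.2 defines the extension set as "based on subjects who received at least one dose of active treatment" in the extension. For continuous endpoints it says: "Continuous efficacy endpoints will be summarized using mean, SD, median, minimum, maximum, and number of observations analyzed". It gives no model, estimand or missing-data rule. The MMRM of Section 9.6.1 uses readings to Week 24 only, and the random-coefficient model for FVC decline sits in Section 9.6.2.1, which covers the 24-week phase. Section 9.1 defers details to a separate SAP, whose text is not in the combined document.

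Section 9.7.2 applies to an absolute fall of 10 or more "from baseline in percent predicted FVC at two consecutive evaluations at a minimum of 4 weeks between evaluations". Such subjects "must be discontinued from the study IP and enter the Post-treatment Observational Follow-up". Baseline is the last value before or on the day of first dose, so the threshold accumulates over 104 weeks. Table 5 footnote g refers to "those subjects who discontinue for progressive disease during the 24-Week Double-blind Placebo-controlled and 80-Week Active Treatment Extension Phases", so stops for progression are expected in both phases. Section 6.3 provides one visit about 28 days after the last dose, with lung function collected for safety only.

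**The concern.** Stopping depends on the outcome, and values after stopping are not collected. The mean at a late visit then describes subjects who have not met the decline rule, not everyone assigned to that dose. A second selection comes at entry: a subject randomized to 200 or 400 mg who stopped before Week 24 for decline, toxicity or death is absent from the extension set, although the change being summarised starts at Baseline.

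To Week 24 the plan uses likelihood models. These can accommodate a stopping rule that acts on recorded FVC, provided the triggering readings are in the model. The extension summaries have no such protection. A reader could take the late means as evidence of a durable effect. If one dose declines faster it also loses more subjects, so the visible gap between doses narrows.

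**Working it through.** **The plan's own figure.** The documents give no figure for the extension. The only input taken from them is the Week 24 SD of 5 in Section 9.3. The power statement there reproduces: 2.2 / (5 × √(2/55)) = 2.31, which at two-sided alpha 0.1 on 108 df gives 74.2% by noncentral t, against the stated 75%.

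**Simulation.** Change from Baseline = slope × time + reading error − baseline reading error, at the Table 5 visits (Weeks 1, 4 to 24 every 4 weeks, 25, 28 to 52 every 4 weeks, 58 to 100 every 6 weeks, 104). A subject leaves after two consecutive evaluations at least 4 weeks apart, both at −10 or below. There is no other dropout.

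*Assumptions not in the documents:* mean decline of 2, 4 or 6 points a year; normally distributed slopes; and the split between slope SD and reading SD. The split is constrained by √((slope SD × 24/52)² + 2 × reading SD²) ≈ 5. For example, slope SD 5.7 and reading SD 3.0 give √(6.92 + 18) = 4.99.

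**Week 104 FVC change: observed-case mean (bias in brackets)**

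| Slope SD per year | 2/yr, true −4 | 4/yr, true −8 | 6/yr, true −12 |
|---|---|---|---|
| 0 (common slope) | −3.3 (0.7) | −6.4 (1.6) | −8.9 (3.1) |
| 2 | −2.6 (1.4) | −5.2 (2.8) | −7.4 (4.6) |
| 3 | −1.7 (2.3) | −4.1 (3.9) | −6.0 (6.0) |
| 4.0 | −0.6 (3.4) | −2.7 (5.3) | −4.5 (7.5) |
| 5.7 | +1.5 (5.5) | −0.4 (7.6) | −2.0 (10.0) |
| 7.66 | +4.3 (8.3) | +2.5 (10.5) | +0.9 (12.9) |

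At slope SD 5.7, 71%, 59% and 46% of subjects are still observed at Week 104. At Week 52 the bias is smaller: true changes of −2, −4 and −6 show as −1.0, −2.4 and −3.8.

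**Difference between doses.** Take one dose declining at 2 a year and the other at 6, a true Week 104 difference of 8. With a common slope the observed difference is −3.3 − (−8.9) = 5.6. With slope SD 5.7 it is +1.5 − (−2.0) = 3.5.

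**Other shapes of decline, at 6 a year (true −12.0).** A Brownian path gives an observed Week 104 mean of −6.1. Exponentially distributed declines with no improvers give −4.3; in that case the Week 24 SD was not held at 5.

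**Which selection matters more.** With a slope SD of 3 points per 24 weeks (3 × 52/24 = 6.5 a year) and decline of 6 a year, the true Week 104 mean is −12.06 in all subjects and −11.51 in extension entrants, and the observed mean is −0.82. Entry selection by the FVC rule contributes 0.55 of the 11.24-point gap; later removal contributes the rest. Early stops for toxicity or death were not simulated. Carrying the last value forward in the same scenario gives −7.2, which is better but still biased.

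**Would a model help?** At the 5.7/3.0 split, a random intercept and slope model fitted to the truncated data returned −4.1 to −4.2 (true −4) and −12.1 to −12.2 (true −12). The data were generated from that same linear model, so this shows only that the FVC rule is recoverable in principle.

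**The case against.** The case against is substantial, and much of it limits the point.

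- *A reader might infer that the late curve looks stable however fast subjects decline.* It does not. Observed means still fall as the decline rate rises, and retention falls with them, which the planned number of observations would show. Flatness depends on slope spread: at 6 a year the true Week 52 to 104 change of −6.0 appears as +2.6 at slope SD 6.5 a year, but as −3.8 with a common slope.
- *A reader might infer that every confirmed decliner is removed.* Section 9.7.2 reads that way. Section 6.2 uses weaker wording and addresses subjects treated for shortness of breath. Section 11.1 lists progression as a sufficient reason and leaves the decision to the treating physician. Partial application would reduce the bias.
- *A reader might infer that the analysis set is limited to subjects still on drug.* It is anyone with one active extension dose. The restriction arises from data collection. An Early Termination visit collects spirometry and 6MWT, and Section 9.6.2.2 does not say how those values enter.
- *A reader might infer a bias floor above the planned effects of 3 and 1.3.* There is none: the table goes down to 0.7. Those effects are also Week 24 differences between arms, not changes within an arm at Week 104.
- *A reader might infer that dose selection is compromised.* Section 9.9.3 rests dose-response primarily on the Week 24 MMRM, and the plan assumes no difference between doses.

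The visible extension endpoints are 6MWT and Borg. Stopping for a 50-metre loss is at the investigator's discretion, so the FVC rule reaches them only through correlation. Section 6.4.3 asserts a strong correlation between 6MWT changes and lung function changes, but gives no value. Section 9.5 already reports reasons for discontinuation by study phase, though not by visit beside the means. Descriptive reporting of an uncontrolled extension is a defensible choice. None of this removes the direction of the bias, which appeared under every set of assumptions tried.

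**Conclusion.** The point holds in limited form. Under Sections 9.6.2.2 and 9.7.2 together, late-visit FVC means are biased toward stability, and a true difference between doses is reduced. The size cannot be fixed from the documents. With the Week 24 SD at 5 and assumed declines of 2 to 6 points a year, the Week 104 bias is about 0.7 to 3.1 points with a common slope and about 5.5 to 10 points at slope SD 5.7 a year; it is larger if slopes vary more. These figures assume that the FVC rule is always applied, that there is no other dropout, and that Early Termination values do not enter the Week 104 mean.

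For 6MWT and Borg a bias in the same direction is expected through correlation with FVC, but it was not quantified. The extension is descriptive, and the Week 24 primary and dose-response analyses are unaffected. The separate SAP may already settle some of the handling. The change is worth making because it uses models the plan already has and data it already collects.

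**What to change.** 1. Keep the descriptive tables in Section 9.6.2.2 and label them as observed cases. State how Early Termination values enter. Beside each visit, print by dose the numbers removed for FVC decline, other discontinuation and death.
2. Wherever FVC is reported beyond Week 24, add as a supportive analysis the random-coefficient model of Section 9.6.2.1 or the MMRM of Section 9.6.1, extended to Week 104. Include all FAS subjects randomized at Baseline to 200 or 400 mg, including those who stopped before Week 24, and the readings that triggered stopping. Fit subjects who switched from placebo separately.
3. For 6MWT and Borg at Weeks 52, 76 and 104, add a sensitivity analysis by multiple imputation with the subject's FVC history as a predictor.
4. Reconcile the wording on stopping in Sections 6.2, 9.7.2 and 11.1, so that it is clear which exits the analysis has to handle.

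The cost is SAP wording and programming, with no new visits or subjects. The downside should be stated in the plan: the estimates rest on missing-at-random for other dropout, and they do not isolate the drug effect, because SOC may be added and there is no placebo arm after Week 24.

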### 9.7. Safety Analysis

The safety analyses for the 24-week Double-blind Placebo-controlled Treatment Phase will be performed using the safety population as defined in Section 9.2 by treatment group. The safety analyses will also be performed for the CC-90001 exposure period for subjects who receive at least one dose of CC-90001, which will include safety data during the 24-week Double-blind Placebo-controlled Treatment Phase and the 80-week Active Treatment Extension Phase. Safety will be assessed by clinical review of all relevant parameters including AEs, laboratory tests, vital signs, and ECG measurements; summary of safety parameters will include data collected at scheduled, unscheduled, and early termination visit, and post-treatment observational follow-up visit. No inferential testing for statistical significance will be performed.

Adverse events will be classified using the MedDRA classification system. All AEs will be summarized by frequency, severity and relationship to IP. Adverse events leading to death or to discontinuation from treatment and serious adverse events will be listed separately. Study drug-related AEs will be listed separately. In the by-subject analysis, a subject having the same event more than once will be counted only once and by greatest severity.

Laboratory data will be summarized by visit descriptively (count, mean, median, standard deviation, and range). In addition, shift tables showing the number of subjects with values below, within and above the normal ranges pretreatment versus post treatment, together with the number determined to be clinically significant, will be provided.

Vital sign measurements, including weight, will be summarized descriptively by visit (count, mean, median, standard deviation, and range).

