## 1.7. Potential Risks of CC-90001 and the Study Population

Based on the Phase 1 studies in healthy subjects and the Phase 1b study in pulmonary fibrosis subjects, the TEAEs associated with administration of CC-90001 are mostly gastrointestinal in nature. Gastrointestinal TEAEs reported in these studies included nausea, diarrhea, indigestion, abdominal discomfort/cramping, emesis, and constipation. Headache, rash, dermatitis, fatigue and musculoskeletal pain TEAEs were also reported. The majority of the reported TEAEs were mild or moderate in severity. Some subjects who experienced nausea in the Phase 1 studies have reported less nausea when the IP was taken with food. There were no SAEs reported in the Phase 1 studies.

The Sponsor has instituted extensive safety monitoring into this protocol based upon potential risks associated with CC-90001 and the disease under study.

- Frequent study visits to assess safety laboratory results, including, but not limited to, liver function, white blood cell (WBC) count, hemoglobin, total cholesterol, high density lipoprotein (HDL), low density lipoprotein (LDL), triglycerides, pulmonary function and arterial oxygen saturation (SpO2).
- Individual subject dose stopping rules and study stopping rules to ensure subjects are discontinued from CC-90001 in the event of severe liver toxicity. In a study conducted with the structurally unrelated pan-JNK inhibitor, CC-930, IPF subjects treated with high doses of CC-930 demonstrated abnormal liver function tests after approximately 8-12 weeks of daily dosing. In order to support this Phase 2 study with chronic dosing, the CC-90001-CP-003 study in pulmonary fibrosis subjects was conducted to understand the safety profile after a 12-week treatment duration.
- CC-90001 may be an inhibitor of liver transporters (eg, OATP1B1 and OATP1B3) and breast cancer resistance protein (BCRP). Therefore, subjects taking statins

concomitantly with CC-90001 may experience increased plasma concentrations of statins with prescribed doses. To ensure the safety of the subjects, concomitant statins will be dose adjusted to a therapeutic level (see Section 8.2.1).

- Urine cytology to examine for abnormal cellular findings.
- Electrocardiograms (ECGs) with centralized over-read and blood pressure measurements will be performed to monitor for potential cardiovascular effects.

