### 4.3. Exclusion Criteria

The presence of any of the following will exclude a subject from enrollment:

1. Subject has any significant medical condition, laboratory abnormality, or psychiatric illness that would prevent the subject from participating in the study
2. Subject has any condition including the presence of laboratory abnormalities, which places the subject at unacceptable risk if he/she were to participate in the study
3. Subject has any condition that confounds the ability to interpret data from the study
4. Significant clinical worsening of pulmonary fibrosis between Screening and Baseline (Visit 2), in the opinion of the Investigator
5. Subjects with any of the following laboratory criteria:
  - White blood cell count (WBC)  $< 3500/\text{mm}^3$  ( $< 3.5 \times 10^9/\text{L}$ ) or  $> 14,000/\text{mm}^3$  ( $> 14 \times 10^9/\text{L}$ )
  - Platelet count  $< 120,000/\mu\text{L}$  ( $< 120 \times 10^9/\text{L}$ )
  - Serum creatinine  $> 1.5 \text{ mg/dL}$  ( $> 132.6 \mu\text{mol/L}$ )
  - Aspartate aminotransferase (AST/SGOT)  $> 1.5 \text{ X}$  upper limit of normal (ULN)
  - Alanine aminotransferase (ALT/SGPT)  $> 1.5 \text{ X}$  upper limit of normal (ULN)
  - Total bilirubin  $> 2 \text{ mg/dL}$  ( $> 34.2 \mu\text{mol/L}$ )
  - Hemoglobin  $< 10 \text{ g/dL}$  ( $< 100 \text{ g/L}$ )
6. Subject with a QTcF  $> 450 \text{ msec}$
7. Any condition other than pulmonary fibrosis that in the opinion of the Investigator is likely to result in the death of the subject within the next year
8. Inability to obtain reproducible, high-quality pulmonary function tests.
9. Evidence of clinically relevant airways obstruction (ie,  $\text{FEV}_1/\text{FVC} < 0.7$ ) at Screening and/or significant respiratory disorder/pathology (eg, pulmonary arterial hypertension requiring treatment, asthma, tuberculosis, sarcoidosis, hypersensitivity pneumonitis, aspergillosis, asbestosis, neoplastic disease, cystic fibrosis or other interstitial lung disease) other than IPF

*Note: Following central readings of HRCTs and central reviews of lung biopsies, if performed, underlying causes of pulmonary fibrosis in subjects enrolled in the PPF substudy may include fibrotic lung diseases other than IPF.*
10. Subject is likely to have lung transplantation during the first 24 weeks of the study (being on transplantation list is acceptable for participation)

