### 11.2. Discontinuation Criteria for Elevation of Hepatic Transaminases

Subjects should be carefully monitored for changes in liver function:

- $ALT > 3 \times$  upper limit of normal (ULN)
- $AST > 3 \times$  ULN

A history of alcohol use and or biliary colic as potential causes of the above findings should be elicited. For subjects experiencing either of the above, use of IP should be interrupted and subjects should undergo repeat testing, including ALT, AST, total bilirubin, and alkaline phosphatase, within 48 to 72 hours of the original test to confirm or refute the finding. If the ALT or AST lab result(s) is confirmed to be  $> 3 \times$  ULN, the subject should not be re-challenged with IP. The subject should be discontinued from the study IP and enter the 4-week Post-treatment Observational Follow-up Phase and hepatic enzyme(s) should be followed until resolution.

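### The visible safety section gives no by-arm count of subjects with ALT or AST above 3 x ULN, although the protocol acts on treatment at that limit

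*Combined protocol and SAP*

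**What the plan says.** Section 9.7 describes laboratory reporting for all analytes together. The one categorical output in the visible text is a set of "shift tables showing the number of subjects with values below, within and above the normal ranges pretreatment versus post treatment". The same sentence adds a count of values judged to be of clinical significance. No number defines clinical significance, and the text does not say which post-treatment value is classified. The same section plans by-visit descriptive statistics that include the range, and adverse event (AE) summaries by frequency, severity and relationship. It also states: "Adverse events leading to death or to discontinuation from treatment and serious adverse events will be listed separately". Data from unscheduled, early termination and follow-up visits are included, and no inferential safety testing is planned.

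Elsewhere the protocol handles ALT and AST as multiples of ULN. Exclusion criterion 5 in Section 4.3 ("Subjects with any of the following laboratory criteria") bars subjects above 1.5 x ULN, so entry between 1 and 1.5 x ULN is allowed. Section 11.2 interrupts investigational product above 3 x ULN and calls for a repeat test within 48 to 72 hours. Once the rise is confirmed, "the subject should not be re-challenged with IP. The subject should be discontinued from the study IP".

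Section 1.7 includes liver toxicity among the potential risks. It reports that subjects on high doses of a structurally unrelated JNK inhibitor "demonstrated abnormal liver function tests after approximately 8-12 weeks of daily dosing". Section 9.9.3 bases the choice of dose for further development on the overall benefit-risk profile of each dose.

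**The concern.** The protocol sets two numerical limits for ALT and AST, and the visible categorical table uses neither. A table with a single class above normal cannot separate a trivial excess from a rise large enough to stop treatment. It shows no movement at all for a subject who enters slightly above normal and then rises sharply.

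What is at stake is the comparison between doses. The study compares 200 mg, 400 mg and placebo, and the dose for further development rests on benefit-risk (Section 9.9.3). The dose for the progressive pulmonary fibrosis substudy also depends on a benefit-risk review (Section 9.8). For a named potential risk with a defined action limit, the direct summary is the number of subjects per arm who crossed that limit. The visible text does not plan it.

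**Working it through.** The plan states no figure on this point, so there is none to reproduce. The check sorts example values into the planned classes and then asks what each other planned output would report.

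**Inputs.** Three shift classes (Section 9.7); entry limit 1.5 x ULN (Section 4.3, criterion 5); action limit above 3 x ULN (Section 11.2); 55 subjects per arm (Section 3.1).

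**Step 1: classification.** Write x for the value as a multiple of ULN. On the upper side, the class is within normal if x ≤ 1 and above normal if x > 1.

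| Baseline to post (x ULN) | Planned cell | Post value above 3 x ULN? |
|---|---|---|
| 0.8 to 1.1 | within to above | no |
| 0.8 to 3.5 | within to above | yes |
| 0.8 to 10 | within to above | yes |
| 1.4 to 1.45 | above to above | no |
| 1.4 to 3.5 | above to above | yes |
| 1.4 to 10 | above to above | yes |

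All six starting values are eligible. The first three pairs fall in one cell. The last three register no shift.

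**Step 2: the other outputs.** Does each give the number of subjects per arm above 3 x ULN?
- *Clinically significant count:* it separates some values, but without a cut-off it need not correspond to 3 x ULN.
- *By-visit range:* it gives one maximum per visit. One subject at 6 x ULN and five subjects at 6 x ULN give the same maximum.
- *AE summaries:* under Section 10.3 a laboratory value that leads to interruption of product is an AE, so a rise handled under Section 11.2 should appear. The same section says that when the abnormality belongs to a diagnosis or syndrome, only the diagnosis is recorded, so cases can spread over several terms. Section 10.2.2 places asymptomatic diagnostic findings under mild, so severity need not track the size of the rise.
- *Discontinuation and serious AE listings:* these show individual cases, not counts by laboratory threshold.

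Each output can reveal a case; none gives the count.

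**Step 3: dilution, on assumed rates.** The documents give no liver event rates. Suppose all subjects enter within normal, a proportion r exceeds 3 x ULN, and a further proportion b rises less. The within-to-above cell then holds 55(b + r) subjects, of whom 55r are above 3 x ULN.
- For r = 2%, 5% and 10%, 55r = 1.1, 2.75 and 5.5. The chance of at least one case, 1 − (1 − r)^55, is 67%, 94% and 99.7%.
- For b = 10%, 20% and 30%, 55b = 5.5, 11 and 16.5 lesser rises.
- The share of the cell above 3 x ULN is r/(b + r). It runs from 2/(30 + 2) = 6% to 10/(10 + 10) = 50%.

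Over this assumed range, cases are likely to occur and would make up between about one in sixteen and one half of the cell that contains them.

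**The case against.** The strongest defence is that the shift table is one output among several. The sentence that defines it also adds the clinically significant count, which is meant to separate minor from important abnormalities. A rise above 3 x ULN managed under Section 11.2 becomes an AE by rule under Section 10.3, not by investigator preference, and AEs are summarized by treatment group. The by-visit range exposes extreme values, and unscheduled retests are included. An external committee reviews unblinded safety data (Section 9.9.4), and a treatment group can be stopped for unacceptable safety (Section 9.8).

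Section 9.1 also says that the statistical section is an outline, with detail left to a separate SAP whose text is not in the file reviewed. The contents list and the body both pass from 9.7 to 9.7.2, so part of the safety section may have been removed. Cut-points for shift tables are ordinary SAP detail.

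Most of this stands. Individual cases would be seen, and subject protection does not depend on this table. It does not supply a by-arm count at the protocol's own limit: the clinically significant count has no cut-off, AE terms and severity do not map to 3 x ULN, and the documents do not say which laboratory tables the committee receives.

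**Conclusion.** The point holds as a reporting gap of moderate weight. The three-class table does not match the 1.5 and 3 x ULN limits that the protocol itself uses, and no visible output counts subjects above 3 x ULN by arm. Step 1 rests only on the stated classes and limits. The shares in Step 3 rest on assumed rates. Sample size, primary analysis, data collection and subject monitoring are not affected. This is a cheap improvement.

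A reader might infer more than the documents support:
- *That the safety analysis cannot show a liver signal.* The limitation belongs to the shift classes; other outputs would reveal cases.
- *That liver toxicity is the protocol's main named risk.* Section 1.7 lists several risks, ties the liver finding to a structurally unrelated compound, and describes events with CC-90001 as mostly gastrointestinal.
- *That recovered subjects would be counted as normal.* That needs a last-value definition, which Section 9.7 does not state; it leaves the post-treatment value undefined.
- *That the dilution can be expressed as a loss of statistical significance.* No safety testing is planned, and the event counts would have to be invented.
- *That the full plan lacks such a table.* The separate SAP could contain it, so its absence is shown only for the visible text.

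**What to change.** For ALT and AST, add a table of baseline class against maximum on-treatment value, unscheduled visits included. Use the classes up to ULN, >1 to 1.5, >1.5 to 3 and >3 x ULN. Present it by treatment group, once for the 24-week double-blind phase and once for the CC-90001 exposure period that Section 9.7 already defines. State which baseline applies in the exposure period to subjects who move from placebo to active treatment at Week 24. Keep the normal-range shift table for the other analytes. If the separate SAP already contains this table, confirming that closes the point.

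The cost is SAP wording and one additional descriptive table. Chemistry is scheduled at every visit in Table 5 and analysed by the central laboratory (Section 6.1), so no new data are needed and no clinical rule changes.
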